A total of 51 participants will be recruited with the goal of 40 participants enrolled. Participants will be randomly assigned 1:1 to either RST (intervention arm) or no active treatment (control arm), which is considered standard of care in this patient population. The participants in the control arm will have no active treatment for 4 weeks and will then participate in RST as a cross-over design. Data obtained will be used to evaluate clinical efficacy and durability. The primary efficacy endpoint is physiologic function metrics of the oropharyngeal swallow, and the secondary endpoint will be respiratory-swallow phase patterning. We will also elaborate on the impact of RST by detailing the physiological, airway protective, and morphometric changes that occur. We will use reproducible, reliable, and validated metrics that include the Modified Barium Swallow Impairment Profile, Penetration-Aspiration Scale, and Computational Analysis of Swallowing Mechanics to distinguish the mechanistic effects of RST. Further, adherence to a novel HP component using self-guided practice will be introduced and tested for feasibility and contribution to the degree and durability of the RST intervention effect.

Our overarching goal is to provide two parallel tracks of knowledge generation: 1) provide immediate clinical translation of experimental findings to improve the lives of Veterans and non-Veterans, and 2) drive model generation on fundamental mechanisms of motor coordination. Basic knowledge will drive clinical application and vice-a-versa. As such, this is an ideal experimental and clinical context that will fuel knowledge generation in this highly significant area of science and clinical practice.

Clinical Impact of Respiratory-Swallow Training on Refractory Dysphagia in OP HNC Funding
(1010498-19)

Specific Aim 1. Directly train optimal respiratory-swallow phase patterning using RST and test the clinical efficacy and durability of the effect measured by change in physiologic metrics of the oropharyngeal swallow. Hypothesis: RST will improve swallow physiology, oral intake status and liquid/food texture tolerances. Primary Outcome: Physiologic metrics of the oropharyngeal swallow as measured by the Modified Barium Swallow Impairment Profile (MBSImP) scores,^{13,14,19}; Secondary Outcome: Functional Oral Intake Scale (FOIS).^{17,18}

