Data Management, Analysis, and Reporting System Overview. Study related data are stored on VA approved computers and the VA research shared drive (S:), including de-identified study-related data (videofluoroscopic images, respiratory traces). Identifiable data (VASA), including demographic data, questionnaire responses, and treatment results are stored on the VA REDCap behind the VA firewall. De-identified videofluoroscopic images and respiratory tracings will be transported via VA issued encrypted external hard drives for analysis by specially trained analytic experts to the PI's lab at Northwestern University, and then stored on and analyzed from a password protected, dedicated server. This server is managed by Northwestern Information Technology and accessible to only approved study personnel. We will update the data transfer and storage operations as we are provided additional guidance and requirements from the ORO, Office of Research Oversight.

Power and Sample Size Justification. A total of 40 subjects will be randomized 1:1 using stratified block randomization to either Respiratory-Swallow Training (RST, intervention arm) or no control arm, where the participants serve as their own control and then cross over into the intervention group. Strata will be defined by treatment type. Data obtained will be used to evaluate clinical efficacy and durability. The primary outcome measure will be MBSImp physiologic function metrics of the oropharyngeal swallow. Our previous preliminary trial that tested the safety and efficacy of the behavioral swallowing intervention in a small sample of Veteran and non-Veteran patient with head and neck cancer showed a positive change in the physiologic outcomes. Assuming a similar treatment effect in the current trial, 20 patients in each arm provides 95% power to detect a change in MBSImp physiologic function in at least one of three MBSImp components (laryngeal vestibular closure, tongue base retraction, and pharyngeal residue) based on a Cochran-Mantel-Haenszel test with two-sided $\alpha = 0.025$. Although dropouts have been rare in our prior studies, we nonetheless inflated our sample size by 10% to adjust for unanticipated attrition, and plan to recruit 20 participants per arm for a total sample size of 40 subjects to guarantee at least 80% power. Thus, our final sample size will be a total of 40 participants.

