MBSImP Scores. The MBSImP scores will provide a primary outcome measure of swallowing impairment. The MBSImP is a validated and reliable scoring system for the quantification of swallowing impairment from MBSS recordings.^{13,14,19} This tool has an ordinal scoring schema that permits quantification of oral, pharyngeal, and esophageal components of swallowing physiology. The operational definitions for the component scores represent a unique and unambiguous observation of structural movement and bolus flow. Seventeen physiologic components will be scored on a previously validated, rank order scale from least to most impaired. The scale for components ranges from 0-2 to 0-4 for each physiologic component.¹⁴ Years of field testing shows scores of 0 or 1 for the physiologic components of lip closure, oral residue, pharyngeal residue, and tongue base retraction are considered to be within normal limits.¹¹² For all other components, scores greater than 0 represent some level of impairment. Two methods will be used for MBSImP scoring: swallow-by-swallow (SS) and overall impression (OI). SS scoring assigns an MBSImP score for all applicable physiologic components for each of the 12 swallowing tasks given during the protocol. SS scores will be recorded for each participant. The highest (worst) score will be given during SS scoring when the participant's condition or performance on a previous swallowing task results in the withholding of a subsequent swallowing task for safety concerns.^{9,52} Additionally, missing data in SS interpretation will result if a participant refuses a swallowing task.⁵² As such, we will only include scores for swallowing tasks that are actually presented.

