5.6 Data Analysis

Statistical Considerations. Specific Aim 1: Trial design. The primary objective of Specific Aim 1 is to demonstrate the clinical efficacy and durability of RST in participants with dysphagia with a history of OP HNC. A total of 88 participants will be [recruited and randomly assigned 1:1 to either RST (intervention arm) or control arm, given the crossover design of the study. We will use a stratified permuted block randomization scheme with random block sizes of 2 or 4 to balance important prognostic variables across the two trial arms. There will be 5 strata defined by treatment modality (radiation therapy alone, surgery alone, chemo-radiation therapy, surgery + post-operative radiation therapy, surgery + post-operative radiation therapy + adjuvant chemotherapy). The study statistician will maintain randomization lists and be responsible for randomizing consented participants. The study schema is depicted in Figure 8. The control arm will cross over to RST after visit 1 following data collection for evaluation of clinical efficacy.

Endpoint Definitions and Analysis Plans. The primary efficacy endpoint for Aim 1 is oropharyngeal swallowing physiologic metrics (MBSImp) and evaluated at: visit 0, defined as pre-RST for intervention subjects, and baseline for control subjects; and visit 1, defined as post-RST for intervention subjects or 4 weeks post-baseline evaluation for control subjects. We will compare changes in MBSImp physiologic function metrics in patients randomized to intervention versus control. Change in MBSImp physiologic function metrics will be compared using one-way analysis of covariance (ANACOVA), with trial arm as the main effect and adjustment for stratification variable of treatment type. If approximate normality is not satisfied, we will use generalized estimating equations (GEEs) with an identity link function and robust standard error estimator. Furthermore, the regression framework of GEEs will accommodate adjustment for stratification factor. Durability of response will be evaluated using ANACOVA or GEEs as described by comparing post-RST MBSImp physiologic function metrics to those obtained at 1-, 3-, and 6-month follow-up visits. We will further evaluate the modifying and confounding effects of sex, age, smoking status, COPD status, and pulmonary function.

[figure not shown]

Figure 7 Study schema for current proposal.

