Further, response durability will be evaluated using FOIS measures obtained at 1-, 3- and 6-months post-RST. Because control subjects cross over to RST at visit 1, FOIS measures collected at visit 1 for control subjects additionally will serve as their pre-RST FOIS measures (Figure 7). Clinical efficacy will be evaluated by comparing change in FOIS (Δ FOIS = FOIS_{visit1} – FOIS_{visit0}) in patients randomized to intervention versus control. Δ FOIS comparisons will be conducted using one-way analysis of covariance (ANACOVA), with trial arm as the main effect and adjustment for stratification variables. If approximate normality is not satisfied, we will use generalized estimating equations (GEEs) with an identity link function and robust standard error estimator, which accommodates valid inference in the presence of misspecification.^{103,104} Furthermore, the regression framework of GEEs will accommodate adjustment for stratification factors. Durability of response will be evaluated using ANACOVA or GEEs as described by comparing post-RST FOIS measurements to those obtained at the 1-, 3- and 6-months follow-up visits. In addition, we will model longitudinally collected FOIS scores as a function of time (measured as a categorical variable) using GEEs, with additional independent variables for stratification factors and pre-RST FOIS included in all models. Comparisons at individual time points will be performed using model-based linear contrasts with inference based on associated two-sided generalized score tests. We will further evaluate the modifying and confounding effects of sex, age, smoking status, COPD status, and pulmonary function. Secondary endpoints include MDADI summary scores, and respiratory-swallow phase patterns (binary measure classified as optimal versus non-optimal) collected at all time points. Analysis of MDADI scores will follow the approach used to analyze FOIS scores. Comparisons between visits 0 and 1 respiratory-swallow phase patterns will be performed using a Rao-Scott chi-square test, an approach that accommodates comparisons of proportions from paired data with Mantel-Haenszel-type adjustments for stratification factors.¹⁰⁵ GEE models of respiratory-swallow phase patterns will be similar to those described for FOIS measures but using instead a

logit or probit link function as appropriate for binary endpoints. Results for all endpoints will be summarized separately for males and females to assess differences by patient sex.

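### The primary MBSImP measure, test and success rule are not fixed, and no multiplicity rule covers the three components on which power is based

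*Combined protocol and SAP*

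**What the plan says.** **Section 5.6, Endpoint Definitions and Analysis Plans.** "The primary efficacy endpoint for Aim 1 is oropharyngeal swallowing physiologic metrics (MBSImp", assessed at visit 0 and visit 1. The test is given as follows: "Change in MBSImp physiologic function metrics will be compared using one-way analysis of covariance (ANACOVA), with trial arm as the main effect", adjusted for cancer treatment type, with an identity-link GEE and robust standard errors if normality fails. No component, total, scoring method, scale, significance level or success rule is named.

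**Section 5.1, Power and Sample Size Justification.** "20 patients in each arm provides 95% power to detect a change in MBSImp physiologic function in at least one of three MBSImp components". The three are laryngeal vestibular closure, tongue base retraction and pharyngeal residue. The test is Cochran-Mantel-Haenszel (CMH) at two-sided 0.025. The paragraph later claims at least 80% power for the same 40 participants.

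**MBSImP Scores (5.1, repeated in 5.6, both under Aim 2).** Seventeen components are scored, and "Two methods will be used for MBSImP scoring: swallow-by-swallow (SS) and overall impression (OI". The Aim 2 statistics add dichotomised components and oral and pharyngeal totals. Nothing says which form serves the Aim 1 primary analysis.

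**Endpoint labels.** The abstract says "the secondary endpoint will be respiratory-swallow phase patterning". The Aim 1 statements make FOIS the secondary outcome. Section 5.6 says "Clinical efficacy will be evaluated by comparing change in FOIS", then lists MDADI and phase pattern as secondary.

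No multiplicity adjustment appears anywhere in the document.

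**The concern.** The power and analysis sections describe different primary analyses. One has three named components, a CMH test and an at-least-one criterion. The other has unspecified metrics, a comparison of mean change and no criterion. A statistician working from 5.6 alone could not tell which number is the primary result, and could settle that after seeing the data.

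The choice matters. Table 3 of the preliminary trial reports 14 MBSImP components. The three in the power paragraph are those that improved with p at or below 0.01, while soft palate elevation worsened (19.8% to 31.0% impaired, p = 0.03). The conclusion can therefore depend on which components count. The power paragraph speaks only of a change, without direction.

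An at-least-one criterion also needs its level split over three tests. A per-test level of 0.025 is the Bonferroni split of 5% over two tests, not three.

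**Working it through.** **Inputs.** From the power paragraph: 20 per arm, two-sided 0.025, three components. From Table 3, percent impaired before and after training: laryngeal vestibular closure 78.2 and 55.5; tongue base retraction 96.0 and 88.6; pharyngeal residue 96.1 and 88.4. From the MBSImP description: 17 components. The correlation between component tests is not given, so a range is assumed.

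**1. The stated 95% power.** The paragraph assumes an effect like that of the preliminary trial. I take the Table 3 pre rate for control and the post rate for RST, one binary outcome per participant (an assumption; the unit is not stated). Power per component is Φ[(d − z·se0)/se1], with d the difference in rates, se0 the pooled and se1 the unpooled standard error.

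For laryngeal vestibular closure at 0.025: d = 0.227, pooled rate 0.6685, se0 = √(0.6685 × 0.3315 × 2/20) = 0.149, se1 = √[(0.782 × 0.218 + 0.555 × 0.445)/20] = 0.144, z = 2.241. Power = Φ(−0.74) = 23.0%. The other two give 8.4% and 8.9%.

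- At least one of three, independent: 1 − 0.770 × 0.916 × 0.911 = 36%.
- Upper bound for any correlation: 23.0 + 8.4 + 8.9 = 40.3%.
- Simulated CMH with five equal strata: 27 to 28%, or 14% with continuity correction.
- 44 per arm (half of the 88 participants stated in 5.6): 67%.

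None gives 95%. About 96 independent observations per arm would, which is 96/20 = 4.8 per participant.

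**2. Error rate, three components at 0.025 each.** Independent: 1 − 0.975³ = 7.3%. Bound for valid tests: 3 × 0.025 = 7.5%. For equicorrelated normal statistics with k tests and c = 2.241, the rate is 1 − ∫φ(u)[Φ((c − √ρu)/√(1−ρ)) − Φ((−c − √ρu)/√(1−ρ))]^k du.

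| Correlation ρ | 3 tests at 0.025 | 17 tests at 0.025 |
|---|---|---|
| 0 | 7.3% | 35% |
| 0.3 | 7.0% | 29% |
| 0.5 | 6.5% | 23% |
| 0.7 | 5.7% | 16% |
| 0.8 | 5.2% | 12% |
| 0.9 | 4.4% | 8% |

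A simulated participant-level CMH test at the Table 3 pre rates gives about 2.7% for any of three. Two components are about 96% impaired, so the discrete test rarely rejects.

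**3. If 0.025 is the overall level.** Each component is tested at 0.025/3 = 0.00833, and the error is at most 2.5%.

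**4. If any of 17 components may count.** At 0.025, independent: 1 − 0.975¹⁷ = 35%; see the last column for other correlations. No section states this as the rule.

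**5. Under a three-way split of 5%.** At 0.0167 each, the error is 1 − 0.9833³ = 4.9% if independent and never above 5%. Power by the method of step 1 is 18.5%, 6.3% and 6.7%, so at least one: 1 − 0.815 × 0.937 × 0.933 = 29%.

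**The case against.** A reader might infer that the three-component criterion lets a positive result arise by chance well above 5%. The documents do not support that. Valid 0.025-level tests cap the rate at 7.5%. It falls below 5% at very high correlation, to about 2.7% for a participant-level CMH test, and to 2.5% if 0.025 is the overall level. The at-least-one wording is also a power statement; no section makes it the decision rule.

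A reader might go further and quote 17 tests at 0.05, which is 1 − 0.95¹⁷ = 58% if independent. The plan states no 0.05 level for this endpoint, only 0.025. The count of 17 may also be too high: the tool covers esophageal components too, while 5.6 confines the primary endpoint to the oropharyngeal swallow. The totals, dichotomised scores and two scoring methods are described under Aim 2, so they are not offered explicitly as Aim 1 primaries.

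Nor is FOIS a second primary endpoint. Both Aim 1 statements call it secondary, and the efficacy sentence in 5.6 is loose wording.

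These objections limit the size, not the defect. Section 5.6 still names no measure, level or success rule, its test differs from the one that was powered, and the meaning of 0.025 is open by a factor of three. Because the Aim 1 text gives no scoring method or scale of its own, the Aim 2 options are the only ones a reader can turn to.

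**Conclusion.** The concern holds as a failure to fix the primary measure, test and success rule, with no multiplicity control. This is more than missing detail: the two sections that should agree on the primary analysis do not, and the primary claim has no defined error rate.

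The size depends on the reading. With 0.025 per component, the error lies between 7.3% (independent) and about 4.4% (correlation 0.9). With 0.025 overall, it is at most 2.5%. It is materially larger, about 35% if independent and 23% at correlation 0.5, only if any of the 17 components may count, which is an assumption. All these figures presume that each test holds its nominal level; whether a robust-variance GEE does so with 40 participants is a further question.

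The 95% power is not reproduced at participant level. The analysis unit, within-participant correlation and control-arm rates are not given, so this shows missing inputs and does not prove the figure wrong.

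**What to change.** In 5.6, define the primary endpoint as change from visit 0 to visit 1 in the three components named in the power paragraph. State one scoring method and one scale, chosen by the sponsor before unblinding; the documents give no ground for preferring either method. Use one test in both the power and analysis sections. Apply Holm at family-wise two-sided 0.05 (steps 0.0167, 0.025, 0.05), or Bonferroni at 0.0167 each. State that success means improvement in at least one component under that rule.

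Treat the other components, totals, PAS and CASM as supportive for the Aim 1 efficacy claim. List FOIS, MDADI and phase pattern as secondary in the same way in the abstract, the aims and 5.6.

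Restate alpha and power under that rule, with the analysis unit, within-participant correlation and assumed control-arm rates. Reconcile the 95% and 80% figures, and the 40 and 88 participants.

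No new data or visits are needed. The cost is in power, and it may not be small: on the participant-level reading above, about 36% at 0.025 becomes 29% at 0.0167, against the stated 95%. If the 95% rests on counting swallows, the plan must say so and allow for clustering within participants.

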Cognitive Criteria. There exists the possibility that study volunteers may experience co-existing cognitive problems that preclude the learning of a new motor task. Participants will be screened immediately following consent (prior to the baseline modified barium swallow study, MBSS) for cognitive impairment using the MoCA⁸⁷ – a cognitive screening test designed to assist health professionals for detection of mild cognitive impairment. The standardized procedure covers the following cognitive domains: visuospatial/executive, naming, memory, attention, language, abstraction, delayed recall, and orientation. Scores for each domain are summed and a total score is obtained that can be adjusted for educational level. MoCA scores < 26 suggest cognitive impairment. Thus, participants with a total MoCA score of 25 or less will be excluded from further participation.

Pulmonary Criteria. There is some evidence indicating that pulmonary function status may impact respiratory-swallow phasing and swallowing impairment,¹¹⁶⁻¹¹⁹ and many patients with HNC present with varying degrees of disordered pulmonary function. An important covariate of upper airway function is lower airway disease. Since smoking is a risk factor for both HNC and COPD, a number of patients have both diagnoses. Although we did not find an association between pulmonary function and the ability to train in our preliminary study, it remains unclear whether expiratory airflow obstruction changes expiratory time constants and potentially impacts swallowing timing or physiology. Consequently, all participants will be screened for the presence of pulmonary disease if they meet the cognitive screening criteria prior to the baseline MBSS. Pulmonary screening will include spirometry performed by a licensed pulmonary function technician and reviewed for compliance with the American Thoracic Society standards.^{117,118} These data will permit further study of the impact of pulmonary function on respiratory-swallow

Clinical Impact of Respiratory-Swallow Training on Refractory Dysphagia in OP HNC Funding (1010498-19)

phasing and the outcome variables in the proposed trial. The best single objective measurement of COPD severity is the forced expiratory volume in 1 second (FEV1).^{120,121} FEV1 will be analyzed as a covariate in analyses. Patients with severe COPD (FEV1<50% predicted) will be excluded from further study and will not receive the baseline MBSS.

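### The between-arm change comparisons leave out the visit 0 score (valid but less precise), and the robust-SE GEE fallback has no small-sample correction for 40 patients

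*Combined protocol and SAP*

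**What the plan says.** **Primary comparison (5.6, Endpoint Definitions and Analysis Plans).** Change in MBSImP from visit 0 to visit 1 is compared between arms by one-way ANACOVA "with trial arm as the main effect and adjustment for stratification variable of treatment type".

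**FOIS and MDADI (5.6).** Change in FOIS is modelled "with trial arm as the main effect and adjustment for stratification variables". For the quality-of-life score, "Analysis of MDADI scores will follow the approach used to analyze FOIS scores".

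**Fallback (5.6).** If approximate normality fails, both comparisons move to "generalized estimating equations (GEEs) with an identity link function and robust standard error estimator". No criterion for the switch is given. No small-sample correction, test statistic or alpha is stated for this comparison.

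**Nearby statements that do not fill the gap.**
- The additional longitudinal FOIS model adjusts for pre-RST FOIS and tests its contrasts "with inference based on associated two-sided generalized score tests". It is a time-course model. For controls the pre-RST value is the one taken at visit 1, so it is not the visit 0 covariate of the between-arm comparison.
- Section 5.4, Pulmonary Criteria, says "FEV1 will be analyzed as a covariate in analyses", without naming a model. FEV1 is in any case not the outcome's own baseline.
- The only alpha, two-sided 0.025, is in the power statement of section 5.1 and belongs to a Cochran-Mantel-Haenszel test.

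**Sample size.** Section 5.1 concludes: "Thus, our final sample size will be a total of 40 participants". Section 5.6 still reads "A total of 88 participants will be" recruited and randomized. That conflict must be reconciled separately; both sizes are used below.

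**The concern.** There are two separate points.

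1. **Precision.** A change score subtracts the baseline with a coefficient fixed at 1. Unless the two visits are almost perfectly correlated, that is not the best coefficient, and estimating it by including the visit 0 score reduces the residual variance. With 20 patients per arm precision is scarce, and the visit 0 value is already collected by design.
2. **Error rate of the fallback.** The robust (sandwich) standard error is justified in large samples. Here the model has 6 coefficients (arm plus 5 stratum means) and 40 patients. Uncorrected, the estimator is too small on average, so the test rejects too often. The switch is a real possibility: FOIS is a 7-level ordinal scale and MBSImP components have three to five levels. If it happens, the false-positive rate of the primary test depends on choices the plan leaves open.

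**Working it through.** **The plan's own figure.** Section 5.1 states 95% power for at least one of three MBSImP components with 20 per arm (Cochran-Mantel-Haenszel, two-sided 0.025). That is a different test from the model examined here. From the pilot rates in Table 3 (78.2→55.5%, 96.0→88.6%, 96.1→88.4%), one observation per patient gives component powers of 23.0%, 8.4% and 8.9%. If the components are independent, 1 − 0.770 × 0.916 × 0.911 ≈ 36%. A figure near 95% appears if about 5 independent swallows per patient are counted (95.9%). The documents do not fix the unit, so the 95% can be neither confirmed nor rejected. Nothing below depends on it.

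**Point 1: precision.** Inputs: 20 per arm (5.1) and 5 strata (5.6). Assumptions: equal SD at both visits, correlation ρ, and an effect of 0.6 SD. Neither ρ nor the effect is in the documents. In units of the single-visit variance:
- change score: 2(1 − ρ)
- with visit 0 as covariate: 1 − ρ²
- ratio: (1 − ρ²) / [2(1 − ρ)] = (1 + ρ)/2
- cost of estimating the slope: factor 1 + 1/(40 − 8) = 33/32

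Power is from the noncentral t distribution, with 34 df for change and 33 df with visit 0 added.

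| ρ | Ratio | Ratio × 33/32 | 40 patients count as (40/ratio) | Power, α 0.05 | Power, α 0.025 |
|---|---|---|---|---|---|
| 0.3 | 0.65 | 0.67 | 62 | 34→48% | 24→36% |
| 0.5 | 0.75 | 0.77 | 53 | 45→55% | 34→43% |
| 0.7 | 0.85 | 0.88 | 47 | 66→72% | 55→61% |
| 0.9 | 0.95 | 0.98 | 42 | 98→99% | 97→97% |

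The gain disappears where (1 + ρ)/2 × 33/32 = 1, that is ρ = 64/33 − 1 = 0.94.

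**Point 2: type I error.** With one change score per patient, an identity-link GEE is ordinary least squares with an uncorrected sandwich variance (HC0). Null trials were simulated at 12,000 per setting (Monte Carlo SE about 0.2 to 0.25 points). Settings: 5 strata, equal or 10/10/40/25/15%; random blocks of 2 or 4; normal or 4-level ordinal scores with latent ρ 0.7. The stratum shares, score distributions and one score per patient are assumptions.

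| Test | n | Nominal 5% | Nominal 2.5% |
|---|---|---|---|
| Planned ANACOVA, t test | 40 | 4.8–5.1% | 2.3–2.6% |
| Fallback, uncorrected Wald z | 40 | 7.8–8.1% | 4.4–4.7% |
| Fallback, generalized score test | 40 | 6.3–6.7% | 3.2–3.5% |
| Leverage-corrected SE (HC2), t reference | 40 | 4.8–5.1% | 2.3–2.7% |
| Visit 0 added, uncorrected Wald z | 40 | 8.2–8.6% | 4.7–5.2% |
| Visit 0 added, corrected SE, t reference | 40 | 4.7–5.4% | 2.4–2.8% |
| Fallback, uncorrected Wald z | 88 | 6.2–6.4% | 3.3–3.5% |
| Fallback, generalized score test | 88 | 5.7–5.8% | 2.8–3.1% |

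HC2 equals the Kauermann-Carroll correction when each patient contributes one observation and the link is the identity.

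A second simulation (20,000 trials per setting, stratum shares 15/10/40/20/15%, and normal, skewed, 7-level ordinal and mostly-zero changes) gave 7.7–7.9% for the Wald test at n = 40. With 36 patients, which is 10% attrition, it gave 8.1–8.5%. At n = 40 the ordinary t test stayed at 4.8–5.0% in every case, including the non-normal ones.

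**The case against.** - **Point 1 is not an error.** True. The change-score analysis is valid, and only efficiency is lost.
- **The gain rests on assumed inputs.** Also true, and for MDADI the pilot suggests it is small. Table 3 gives 60.4 ± 14.8 before and 65.3 ± 16.7 after, p = 0.003. Assuming a paired t test on n patients, the SD of change is 4.9√n/t, and ρ = (14.8² + 16.7² − SD²)/(2 × 14.8 × 16.7). For an assumed n of 15 to 40 this gives ρ of about 0.95 to 0.81. With those SDs in the RST arm and an unchanged SD in controls, the variance ratio after the slope cost is 0.99–1.03, so there is no real gain. At n = 60, ρ is 0.70 and the ratio 0.93. This stands for MDADI. It says nothing about MBSImP, the primary endpoint, or FOIS, whose correlations are unknown. The 0.6 SD effect likewise only illustrates.
- **The authors already adjust for a baseline.** They do, but in the separate longitudinal model and with pre-RST FOIS. That shows they write the covariate out when they intend it.
- **Point 2 is conditional.** It needs normality to fail and an uncorrected test to be used. If the score test named for the longitudinal contrasts carries over, the excess at nominal 2.5% is only 0.7 to 1.0 points. It shrinks but does not vanish.
- **One score per patient is assumed.** Section 5.1 also describes scoring swallow by swallow over 12 tasks. The plan does not fix the unit, so the simulated rates indicate size and should not be read to a tenth of a point.

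**Conclusion.** Both points hold, and both are of moderate weight.

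The planned ANACOVA is unbiased and keeps its level. Omitting the visit 0 score costs precision unless ρ is near 0.94 or higher. At ρ between 0.3 and 0.7 the loss is equivalent to treating 47 to 62 patients' worth of information as 40, before the small slope cost. At 0.9 it is negligible, and MDADI may be in that region.

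The fallback as written over-rejects at 40 patients: about 8% at nominal 5% and about 4.5% at nominal 2.5% with the Wald test, and 6.3–6.7% and 3.2–3.5% with the score test. At 88 patients the excess is smaller but still present with the Wald test. These figures apply only if the fallback is used without a correction, and they assume one score per patient.

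**What to change.** 1. In the between-arm comparisons of MBSImP, FOIS and MDADI, add the visit 0 value of the same outcome as a covariate beside arm and treatment-type stratum, in both the ANACOVA and the GEE version. State which models include FEV1.
2. For the GEE fallback, name the test and alpha, and specify a small-sample-corrected robust standard error (for example Kauermann-Carroll) with a t reference distribution. A stratified randomization test would be an alternative.
3. Make the two changes together. Adding a coefficient without the correction raises the uncorrected Wald error slightly, to 8.2–8.6% at nominal 5%.

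The cost is SAP wording, one more coefficient, and slightly wider intervals if the fallback is used. No new data, visits or patients are needed.
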